8.1.6 Dose Resumption

Patients may resume treatment with NM21-1480 when the TRAEs resolve(s) to Grade ≤ 1 or baseline within 35 days (i.e., 2 missed doses + 7 days in settings with intended biweekly dosing events) or within 49 days (i.e., 2 missed doses + 7 days in settings with intended dosing events every three weeks) from the scheduled dosing, with the following exceptions:

- Patients may resume treatment in the presence of Grade 2 fatigue, alopecia, skin rash.
- Patients who have not experienced a Grade 3 treatment-related skin AE may resume treatment in the presence of Grade 2 skin toxicity.
- Patients with baseline Grade 1 AST/ALT or total bilirubin who require dose delays for reasons other than a 2-grade shift in AST/ALT or total bilirubin may resume treatment in the presence of Grade 1 AST/ALT or total bilirubin.
- Patients with combined Grade 2 AST/ALT and total bilirubin values meeting discontinuation parameters should have treatment permanently discontinued.
- Treatment-related pulmonary toxicity, diarrhea, or colitis must have resolved to baseline before treatment is resumed. Patients with persistent Grade 1 pneumonitis after completion of a steroid taper over at least 1 month may be eligible for re-treatment if discussed with and approved by the Medical Monitor.

- Treatment-related endocrinopathies adequately controlled with only physiologic hormone replacement may resume treatment.

Two dosing delays due to toxicity will be permitted.

In the event of a third occurrence of a toxicity which would require dosing delay, study therapy may be discontinued permanently after consultation with the Sponsor monitor.

8.1.7 Management of Infusion-Related Reactions

Infusion-related reactions may occur during or after administration of NM21-1480. Dose reductions, other than a decrease in the infusion rate, are not allowed. Management guidelines for infusion reactions are displayed in [Table 8-1](#).

Table 8-1 Management of Infusion-related Reactions

NCI CTCAE Grade	Treatment	Premedication at Subsequent Dosing
Grade 1 Mild reaction; infusion interruption not indicated; intervention not indicated	
Increase monitoring of vital signs as medically indicated until the symptoms have resolved.
 
The infusion rate of study drug/study regimen may be decreased by 50% or temporarily interrupted until resolution of the event.
	
Patient may be pre-medicated at the discretion of the Investigator as per institutional norm or consider premedication 1.5 hours (\pm 30 minutes) prior to infusion of NM21-1480 with:
 
• Diphenhydramine 50 mg orally (or equivalent dose of antihistamine)• Acetaminophen (Paracetamol) 500-1000 mg orally (or equivalent dose of antipyretic)
Grade 2 Requires infusion interruption but responds promptly to symptomatic treatment (e.g., antihistamines, NSAIDs, narcotics, IV fluids); prophylactic medications indicated for \leq 24 hours	
Stop infusion and monitor symptoms.
 
Additional appropriate medical therapy may include but is not limited to: IV fluids, antihistamines, NSAIDs, acetaminophen, and narcotics.
 
Increase monitoring of vital signs as medically indicated until the symptoms have resolved.
 
If symptoms resolve within 1 hour of stopping IP infusion, the infusion may be restarted at 50% of the original infusion rate (e.g., from 100 to 50 mL/hour). Otherwise, dosing will be held until symptoms resolve and the participant should be pre-medicated for the next scheduled dose.
 
Participants who develop Grade 2 toxicity despite adequate premedication should be permanently discontinued from further IP administration.
	
Patient should be pre-medicated as per institutional norm or consider premedication 1.5 hours (\pm 30 minutes) prior to infusion of NM21-1480 with:
 
• Diphenhydramine 50 mg orally (or equivalent dose of antihistamine)• Acetaminophen (Paracetamol) 500-1000 mg orally (or equivalent dose of antipyretic)

NCI CTCAE Grade	Treatment	Premedication at Subsequent Dosing
Grade 3 or 4 Grade 3: Prolonged (i.e., not rapidly responsive to symptomatic medication and/or brief interruption of infusion); recurrence of symptoms following initial improvement; hospitalization indicated for other clinical sequelae (e.g., renal impairment, pulmonary infiltrates) Grade 4: Life-threatening; pressor or ventilatory support indicated	
Stop infusion immediately.
 
Begin an IV infusion of normal saline and treat the patient as per institutional norms or consider treating the patient as follows: Recommend bronchodilators, epinephrine 0.2 to 1 mg of a 1:1,000 solution for subcutaneous administration or 0.1 to 0.25 mg of a 1:10,000 solution injected slowly for IV administration, and/or diphenhydramine 50 mg IV with methylprednisolone 100 mg IV (or equivalent), as needed. Patient should be monitored until the Investigator is comfortable that the symptoms will not recur.
 
Additional appropriate medical therapy may include but is not limited to: IV fluids, antihistamines, NSAIDs, acetaminophen, narcotics, oxygen, pressors, corticosteroids, and epinephrine.
 
Increase monitoring of vital signs as medically indicated until the participant is deemed medically stable in the opinion of the Investigator.
 
Hospitalization may be indicated.
 
Participant is permanently discontinued from further IP administration.
	Permanently discontinue dosing

Abbreviations: IP = Investigational product; IV = Intravenous; NCI CTCAE = National Cancer Institute Common Terminology Criteria for Adverse Events, NSAID = Nonsteroidal anti-inflammatory drug

8.2 Study Treatment Packaging and Labelling

8.2.1 Packaging

Prior to addition of the IP, 0.02% poloxamer 188 will be added to the diluent sodium chloride for injection, USP (0.45% or 0.9% dependent on the dose level). Ten (10) mL of the product will be filled into 20R type I glass vials from which the required dose volume will be injected into suitable infusion bags or administered by perfusion syringes, dependent on dose level. The intended clinical dosing frequency is once every other week, or every third week (if applicable) in optional Part A-2 and Part B, over 60-90 minutes through an IV line containing a sterile, non-pyrogenic, low protein-binding inline filter (pore size of 0.2 micron). Additional details can be found in the study Pharmacy Manual.

8.2.2 Storage

All IP supplies for this study must be stored under refrigerated conditions (2°C to 8°C) per storage conditions stated on the IP label. Until dispensed for administration to patients, the study drug will be stored in a securely locked area, accessible to authorized personnel only. Details can be found in the study Pharmacy Manual.

8.3 Patient Compliance

The dosage, timing and mode of administration of study medication may not be changed. Any departures from the intended regimen must be recorded in the eCRF. Study medication accountability and patient compliance will be documented throughout the study/treatment periods using study-specific medication administration record forms. If a participant does not receive the scheduled dose, every effort should be made to administer the dose as soon as possible. Deviations from the intended regimen include:

- receiving unscheduled dose of study drug
- missing a dose
- receiving the incorrect dose

8.4 Study Treatment Accountability

Records shall be maintained of the delivery of study treatment(s) to the study site(s), the inventory at the study site(s), the use of each participant and the return to the Sponsor.

These records shall include dates, quantities, batch numbers, expiry dates and the unique code numbers assigned to the study medication and to the study participants.

The Investigator shall be responsible for ensuring that the records adequately document that the participants were provided the doses specified in the protocol and that all study medication received from the Sponsor is reconciled.

8.5 Concomitant Therapy

8.5.1 Permitted Medications

Patients are permitted the use of topical, ocular, intra-articular, intranasal, and inhalational corticosteroids (with minimal systemic absorption). Steroid doses <10 mg daily prednisone or equivalent (e.g. for adrenal replacement) are permitted. A course of corticosteroids for prophylaxis for contrast dye allergy is allowed.

Bone modifying agents, including bisphosphonates and denosumab, should be used in accordance with label indications as appropriate for patients with bone metastases.

Colony stimulating factors (G-CSF, GM-CSF, erythropoietin stimulating agents, etc.) should not be administered prophylactically. Interventional use of these agents is permitted for the treatment of adverse events.

Palliative and supportive care measures should be administered at the discretion of the Investigator in accord with standards of care.

NM21-1480 may impact CYP enzyme production and activity via cytokine modulation. For this reason, there may be a risk of drug interactions and concomitant medications that are narrow therapeutic index substrates for CYP enzymes should be used with caution and appropriate monitoring.

8.5.2 Prohibited Medications

The following medications and therapies are not permitted during the study from signature of informed consent:

- Other investigational agents or investigational device.
- Any other systemic or localized antineoplastic therapy. Palliative radiation therapy may be permitted for pain or severe symptom control (i.e., radiation for pain control of bony metastases) after discussion with the study Medical Monitor. Radiation will be limited to non-target lesions only.
- Any botanical preparation (e.g., herbal supplements or traditional Chinese medicines) intended to treat the disease under study or provide supportive care. Use of marijuana and its derivatives for treatment of symptoms related to cancer or cancer treatment are permitted if obtained by medical prescription or if its use (even without a medical prescription) has been legalized locally
- Medications or substances known to cause elevation of liver enzymes, including e.g., acetaminophen (a daily dose of up to 2 g/day is allowed to manage acute pain), or systemically active cannabidiol (CBD); topical CBD is allowed
- Immunosuppressive medication including immunosuppressive doses of systemic steroids or absorbed topical steroids (doses >10 mg/day prednisone or equivalent). However, continued treatment with NM21-1480 of a patient on doses \leq 10 mg/day prednisone or equivalent that were initiated for treatment of an AE/irAE within the study is allowable if that AE/irAE has improved to \leq Grade 1 in severity or baseline and continued NM21-1480 treatment is considered in the best interest of the patient as per investigator judgement and following consultation with the Medical Monitor.

9 STUDY ASSESSMENTS AND PROCEDURES

9.1 Clinical Activity Assessments

9.1.1 Tumor Response

Tumor response will be evaluated by the Investigator according to RECIST 1.1 using measurement such as computed tomography (CT) scan (with IV contrast, chest, abdomen, and pelvis) or MRI in case of IV contrast contraindication. In Part B, tumor response will also be evaluated by the investigator according to iRECIST and response assessment for RECIST1.1 and iRECIST will be independently determined by central reading of images, while decisions on continuation of treatment will be based on the investigator's RECIST1.1 and iRECIST assessment. Response assessments will be performed by the Investigators at the end of each assessment cycle to document eligibility for entry into the next treatment cycle. Also, if applicable (see [Table 7-1](#) and [Table 7-2](#), footnote v.), response assessment will be performed at Follow-up Visit 1 (0 to 30 days after discontinuation), Visit 2 (60±7 days after discontinuation), and/or Visit 3 (90±7 days after discontinuation).

Copies of scans will be collected and stored at Medpace in Part A and optional Part A-2. In part B, copies of scans will also be sent to Medpace for independent determination of RECIST1.1 and iRECIST assessments. A detailed description of the central read process can be found in the imaging charter.

Sites are also requested to attempt gathering and submitting the last pre-baseline scans for a patient as part of the tumor-specific therapy history; inavailability of these pre-baseline scans do however not make a patient ineligible for the study.

The same technique (CT/MRI) used at baseline will be utilized throughout the study for a given patient. Computed tomography is the imaging modality of choice for chest/abdomen/pelvis. Brain scans during Treatment and Follow-up periods are required only if there is a prior history of lesions present at Screening, or as clinically indicated. If required, subsequent brain CT scans/MRI should be repeated at assessment cycles 1, 2, etc., and at Follow-up Visit 2. Bone scans at baseline or subsequent visits will be performed only if clinically indicated. If required, subsequent bone scans should be repeated every other assessment cycle (end of assessment cycles 2, 4, 6, etc.) and a single scan at Follow-up Visit 2 or 3.

The timing and frequency of clinical activity assessments are described in [Table 7-1](#) and [Table 7-2](#).

Additional assessments of overall survival (OS) and progression-free survival (PFS) will be assessed by the Kaplan-Meier method (described in [Section 10.6.2](#)).

While conducting the study, tumor response assessment will be done locally, CT/MRI scans will also be stored centrally. During the study, i.e., on an ongoing basis while enrollment into Part B is ongoing and/or at the end of Part B, the Sponsor will re-confirm response assessment by a central

reader blinded to assigned NM21-1480 dose levels (all B cohorts) and treatment assignment (Cohort B5).

9.2 Safety Assessments

At Screening, a medical history will be obtained to capture relevant underlying conditions and prior medications will be collected. The Screening examinations will include hepatitis B and C test, HIV tests, CD4 T-cell count (only for patients who are HIV positive at Screening), and height within 28 days prior to the administration of the first dose of study drug.

Safety assessments including weight, ECOG performance status, ECG (12-lead), vital signs, complete physical examination, limited physical examination, oxygen saturation, concomitant medications, AEs, hematology, serum chemistry, urinalysis, TSH and T4, and pregnancy tests, will be performed as noted in the Schedule of Assessments.

The timing and frequency of safety assessments are described in [Table 7-1](#) and [Table 7-2](#).

9.2.1 Definitions

The definition of AEs, TEAEs, and SAEs is given below. The Investigator and any qualified designees are responsible for detecting, documenting, and recording events that meet the definition of an AE or SAE and remain responsible for following up AEs that are serious, considered related to the study drug or study procedures, or that causes the participant to discontinue the study drug/study.

9.2.1.1 Adverse Events

An AE is defined as any untoward medical occurrence in a participant, or clinical investigation participant administered a pharmaceutical product, and which does not necessarily have a causal relationship with this treatment. An AE can therefore be any unfavorable and unintended sign, symptom or disease temporally associated with the use of a medicinal (investigational) product, whether or not related to the medicinal (investigational) product.

9.2.1.2 Events Meeting the AE Definition

- Any abnormal laboratory test results (hematology, clinical chemistry, or urinalysis) or other safety assessments (e.g., ECG, radiological scans, vital signs measurements), including those that worsen from baseline, considered clinically significant in the medical and scientific judgement of the Investigator (i.e., not related to progression of underlying disease).
- Exacerbation of a chronic or intermittent pre-existing condition including either an increase in frequency and/or intensity of the condition.
- New conditions detected or diagnosed after study drug administration even though it may have been present before the start of the study.
- Signs, symptoms, or the clinical sequelae of a suspected drug-drug interaction.

- Signs, symptoms, or the clinical sequelae of a suspected overdose of either study drug or a concomitant medication. Overdose per se will not be reported as an AE/SAE unless it is an intentional overdose taken with possible suicidal/self-harming intent. Such overdoses should be reported regardless of sequelae.
- "Lack of efficacy" or "failure of expected pharmacological action" per se will not be reported as an AE or SAE. Such instances will be captured in the efficacy assessments. However, the signs, symptoms, and/or clinical sequelae resulting from lack of efficacy will be reported as AE or SAE if they fulfill the definition of an AE or SAE.

9.2.1.3 Events NOT Meeting the AE Definition

- Any clinically significant abnormal laboratory findings or other abnormal safety assessments, which are associated with the underlying disease, unless judged by the Investigator to be more severe than expected for the participant's condition.
- The disease/disorder being studied or expected progression, signs, or symptoms of the disease/disorder being studied, unless more severe than expected for the participant's condition.
- Medical or surgical procedure (e.g., endoscopy, appendectomy): the condition that leads to the procedure is the AE.
- Situations in which an untoward medical occurrence did not occur (social and/or convenience admission to a hospital).
- Anticipated day-to-day fluctuations of pre-existing disease(s) or condition(s) present or detected at the start of the study that do not worsen.

9.2.1.4 Serious Adverse Event

If an event is not an AE per definition above, then it cannot be an SAE even if serious conditions are met (e.g., hospitalization for signs/symptoms of the disease under study, death due to progression of disease).

An SAE is defined as any untoward medical occurrence that:

- Results in death. The cause of death is the AE, death is an outcome.
- Is life-threatening. The term 'life-threatening' in the definition of 'serious' refers to an event in which the participant was at risk of death at the time of the event. It does not refer to an event, which hypothetically might have caused death, if it were more severe.
- Requires in-patient hospitalization or prolongs existing hospitalization. In general, hospitalization signifies that the participant has been detained (usually involving at least an overnight stay) at the hospital or emergency ward for observation and/or treatment that would not have been appropriate in the physician's office or outpatient setting. Complications that

occur during hospitalization are AEs. If a complication prolongs hospitalization or fulfills any other serious criteria, the event is serious. When in doubt as to whether 'hospitalization' occurred or was necessary, the AE should be considered serious.

- Results in persistent or significant disability/incapacity. The term disability means a substantial disruption of a person's ability to conduct normal life functions. This definition is not intended to include experiences of relatively minor medical significance such as uncomplicated headache, nausea, vomiting, diarrhea, influenza, and accidental trauma (e.g., sprained ankle) which may interfere with or prevent everyday life functions but do not constitute a substantial disruption.
- Is a congenital anomaly/birth defect.
- Is an important medical event. Important medical events that may not result in death, be life-threatening or require hospitalization may be considered a serious adverse drug experience, when based on appropriate medical judgement, they may jeopardize the participant or the participant may require medical or surgical intervention to prevent one of the outcomes listed in this definition. Examples of such events include invasive or malignant cancers, intensive treatment in an emergency room or at home for allergic bronchospasm, blood dyscrasias or convulsions that do not result in hospitalization, or development of drug dependency or drug abuse. Patients will be required to permanently discontinue NM21-1480 for the following TRAEs:
 - Any Grade 2 TRAE uveitis, eye pain or blurred vision that does not respond to topical therapy and does not improve to Grade 1 severity within the re-treatment period OR requires systemic treatment.
 - Any Grade 3 non-skin, TRAE lasting >7 days, with the following exceptions:
 1. Grade 3 TRAE uveitis, pneumonitis, bronchospasm, hypersensitivity reaction, or infusion reaction of any duration requires discontinuation.
 2. Grade 3 TRAE endocrinopathies adequately controlled with only physiologic hormone replacement do not require discontinuation.
 3. Grade 3 TRAE laboratory abnormalities not requiring medical treatment or hospitalization do not require treatment discontinuation except:
 - a. Grade 3 TRAE thrombocytopenia >7 days or associated with clinically significant bleeding requires discontinuation.
 - b. Any TRAE liver function test abnormality that meets the following criteria requires discontinuation:
 - i. AST or ALT >5-10 × ULN for >2 weeks or AST or ALT >10 × ULN.

- ii. Total bilirubin $>5 \times$ ULN.
- iii. Concurrent AST or ALT $>3 \times$ ULN and total bilirubin $>2 \times$ ULN without initial finding of cholestasis (elevation of alkaline phosphatase [ALP]).
- iv. For patients with hepatic metastases: AST or ALT $>8 \times$ ULN or AST or ALT $>5 \times$ ULN for ≥ 14 days.
- Any patient experiencing a Grade 4 toxicity or laboratory abnormality must be permanently discontinued.
- Any event that leads to delay in dosing lasting >35 days (i.e., 2 missed doses + 7 days in settings with intended biweekly dosing events) or >49 days (i.e., 2 missed doses + 7 days in settings with intended dosing events every three weeks) from the scheduled dosing requires discontinuation, with the following exceptions:
 1. Dosing delays to allow for prolonged steroid tapers to manage TRAEs may be allowed if approved by the Medical Monitor. Prior to re-initiating treatment in a patient with a dosing delay lasting >35 days (i.e., 2 missed doses + 7 days in settings with intended biweekly dosing events) or >49 days (i.e., 2 missed doses + 7 days in settings with intended dosing events every three weeks) from the scheduled dosing, the Medical Monitor must be consulted. Tumor assessments should continue as per-protocol even if dosing is delayed. Periodic study visits to assess safety and laboratory studies should also continue every 2 weeks or more frequently if clinically indicated during such dosing delays.
 2. Dosing delays lasting >35 days (i.e., 2 missed doses + 7 days in settings with intended biweekly dosing events) or >49 days (i.e., 2 missed doses + 7 days in settings with intended dosing events every three weeks) from the scheduled dosing that occur for non-drug-related reasons may be allowed if approved by the Medical Monitor. Prior to re-initiating treatment in a patient with a dosing delay lasting 35 days (i.e., 2 missed doses + 7 days in settings with intended biweekly dosing events) or 49 days (i.e., 2 missed doses + 7 days in settings with intended dosing events every three weeks), the Medical Monitor must be consulted. Tumor assessments should continue as per-protocol even if dosing is delayed. Periodic study visits to assess safety and laboratory studies should also continue every 2 weeks or more frequently if clinically indicated during such dosing delays.

Patients who meet toxicity related discontinuation criteria discussed above or presented in [Appendix VI](#), (management of irAEs) may be permitted to remain on therapy if the benefits are

considered to outweigh the risks of continued treatment after discussion between the Sponsor and Investigator and between the Investigator and the patient.

In case of development of a \geq Grade 3 (CTCAE V5.0) intolerance or AE related to NM21-1480 that precludes further treatment with the study drug, but patient does not have worsening progression: Patients will complete the remaining visits of their current treatment cycle (without infusions) if possible. Patients will then enter the Follow-up period.

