Resumption of NM21-1480 administration for patients experiencing DLTs may be permitted according to the criteria described under Section “Dose Resumption”, if clinically appropriate, contingent on the return of the DLT to \leq Grade 0-1 severity or to baseline, and interruption or delay of treatment for no more than 35 days (i.e., 2 missed doses + 7 days) from the scheduled dosing and upon discussion with and approval by the Medical Monitor.

The following events shall not be regarded as a DLT:

- Grade 3 AE of tumor flare (defined as local pain, irritation, or rash localized at sites of known or suspected tumor) present for less than 7 continuous days
- Grade 3 Infusion-related reaction resolving within 6 hours and controlled with medical management
- Transient (≤ 6 hours) Grade 3 influenza-like symptoms or pyrexia controlled with medical management
- Grade 3 local reaction or headache that resolves to a maximal severity of Grade 1 within 24 hours
- Grade 3 skin toxicity, or increase liver enzyme (AST, ALT) that resolves to a maximum severity of Grade 1 within 7 days after initiation of medical management (e.g., immunosuppressant treatment)
- Grade 3 skin toxicity that improves to Grade 0 to 2 within 3 days

- Grade 3+ amylase or lipase elevation not associated with symptoms or clinical manifestations of pancreatitis does not represent a DLT
- Grade 3 treatment-related endocrinopathy AEs, such as adrenal insufficiency, adrenocorticotropic hormone (ACTH) deficiency, hyper- or hypothyroidism, or glucose intolerance, which resolve or are adequately controlled with physiologic hormone replacement (corticosteroids, thyroid hormones) or glucose-controlling agents, respectively
- Grade 3 laboratory abnormalities that improve to \leq Grade 2 within 3 days only if asymptomatic and if medical intervention was not required

Elevations of ALT/AST that are >3 -fold above baseline are to be considered adverse events of special interest (AESI) and to be reported with SAE timelines. The details on how to handle this situation are described in [Appendix VI](#), Section “Hepatitis”. In case of Grade 3+ hepatotoxicity, an initial ultrasound or image needs to be done to visualize the biliary tree and to rule out disease progression or occurrence of gall stones.

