Hypophysitis	Headache refractory to nonsteroidal anti-inflammatory drugs or other analgesics; weakness; fatigue, weight gain or weight loss; changes in mood or behavior; hypotension; electrolyte disturbances; abdominal pain; loss of libido; adrenal crisis; hypogonadism	Clinical chemistry tests Endocrinologic laboratory test, ACTH, thyroid function test, MRI of the brain: enlargement of the pituitary with variable contrast enhancement characteristics	Grade 2 without adrenal crisis: high-dose corticosteroids (methylprednisolone 1 to 2 mg/kg/day or the equivalent); initiate appropriate hormone replacement therapy; consultation with an endocrinologist	Withhold NM21-1480 until resolved to ≤Grade 1
			≥Grade 3 or adrenal crisis: high-dose corticosteroids (methylprednisolone 1 to 2 mg/kg/day or the equivalent); consultation with an endocrinologist	Permanent discontinuation from the study
Nephritis	Hematuria, peripheral edema, elevated serum creatinine	Clinical chemistry tests Urine test Biopsy if necessary	Grade 2: administration of corticosteroids at a dose of 1-2 mg/kg/day prednisone equivalents	Withhold NM21-1480 until resolved to ≤Grade 1
			≥Grade 3: administration of corticosteroids at a dose of 1-2 mg/kg/day prednisone equivalents	Permanent discontinuation from the study

irAE	Potential signs and symptoms	Diagnosis and differential diagnosis	Recommended management	Dose modification
Hypothyroidism/ hyperthyroidism	Typically asymptomatic and is identified by lab tests	T3, T4, TSH test results	Asymptomatic \leq Grade 2 hypothyroidism: thyroxine replacement therapy	Continue dosing
			Asymptomatic \leq Grade 2 hyperthyroidism: consider beta blockade	Continue dosing
			\geq Grade 3 hypothyroidism: replacement therapy	Withhold NM21-1480 until resolved to \leq Grade 1 or baseline
			Grade 3 hyperthyroidism lasting \geq 6 weeks despite active management via administration of corticosteroids at a dose of 1-2 mg/kg/day prednisone equivalents	Withhold NM21-1480 until resolved to \leq Grade 1
			Grade 4 hyperthyroidism	Permanent discontinuation from the study

irAE	Potential signs and symptoms	Diagnosis and differential diagnosis	Recommended management	Dose modification

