Dermatitis	Maculopapular rash or erythroderma, pruritus, skin ulceration, bullous dermatitis, Stevens-Johnson syndrome	
Unless an alternative etiology is identified, it should be considered immune-related
 
Pathologic evaluation of skin biopsy can be performed to rule out alternative etiology
	
\leqGrade 2 (up to 30% of body surface area): topical corticosteroids and oral over-the-counter antihistamines and systemic corticosteroids if no improvement within 7 days
	Continue dosing
			
Grade 3 (>30% of body surface area): administration of corticosteroids at a dose of 1-2 mg/kg/day prednisone equivalents
	Withhold NM21-1480 until resolved to \leq Grade 2
			
Grade 4 (Stevens-Johnson syndrome, toxic epidermal necrosis, full-thickness dermal ulceration, necrosis or hemorrhage): high-dose corticosteroids (2-4 mg/kg/day IV methylprednisolone); in-patient hospitalization; consultation with a dermatologist
	Permanent discontinuation from the study
Neuromuscular toxicity	Peripheral sensory neuropathy, muscle weakness, Guillain-Barre syndrome, transverse myelitis, myasthenia gravis	
Physical exam of sensory change, loss of deep-tendon reflexes
 
Neuroimaging, nerve conduction exam,
	
\leqGrade 2: administration of corticosteroids at a dose of 1-2 mg/kg/day prednisone equivalents
	Withhold NM21-1480 until resolved to \leq Grade 1

irAE	Potential signs and symptoms	Diagnosis and differential diagnosis	Recommended management	Dose modification
		Nerve/muscle biopsy	≥Grade 3: high-dose corticosteroids (2-4 mg/kg/day IV methylprednisolone)	Permanent discontinuation from the study
Ocular toxicity	Photosensitivity, pain or dryness of the eyes, blurred vision, uveitis, iritis, episcleritis	ophthalmic exam	≤Grade 2: topical steroids (1% prednisolone)	Withhold NM21-1480 until resolved to ≤Grade 1; if not resolved ≤Grade 1 within 14 days with topical steroids or initiation of systemic treatment, permanent discontinuation from the study
			≥Grade 3: high-dose systemic corticosteroids (2-4 mg/kg/day IV methylprednisolone)	Permanent discontinuation from the study
Other irAEs, such as arthritis, pancreatitis, hemolytic anemia, adrenal insufficiency, myasthenic syndrome, and rhabdomyolysis			Grade 2	Withhold NM21-1480 until resolved to ≤Grade 1
			≥Grade 3	Permanent discontinuation from the study

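### For Grade 3 adrenal insufficiency controlled on hormone replacement, the protocol body lets treatment continue but Appendix VI stops it permanently; asymptomatic Grade 4 amylase or lipase has a similar clash

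*Protocol*

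**What the plan says.** **Adrenal insufficiency.** Protocol section 9.2.1.4 lists the treatment-related events that end NM21-1480 treatment for good. Its general Grade 3 rule is "Any Grade 3 non-skin, TRAE lasting >7 days, with the following exceptions", and one of those exceptions is "Grade 3 TRAE endocrinopathies adequately controlled with only physiologic hormone replacement do not require discontinuation". Section 8.1.6 sets the recovery needed before a restart and then makes its own exception: "Treatment-related endocrinopathies adequately controlled with only physiologic hormone replacement may resume treatment". Section 7.2.5.1 gives adrenal insufficiency and ACTH deficiency as examples of Grade 3 endocrinopathies that do not count as DLTs once they resolve or are controlled on replacement. Appendix VI (section 18.6) ends with a row for "Other irAEs, such as arthritis, pancreatitis, hemolytic anemia, adrenal insufficiency, myasthenic syndrome, and rhabdomyolysis". For that row the drug is held at Grade 2 and permanently discontinued at Grade 3 or above.

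**Amylase and lipase.** Section 8.1.5.2 says that related elevations of Grade 3 or higher, without signs of pancreatitis, need no dose delay, and asks that the Medical Monitor be consulted. Section 9.2.1.4 requires permanent discontinuation for any Grade 4 toxicity or laboratory abnormality.

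**Links between the lists.** Section 8.1.5 refers the reader to Appendix VI for further detail on irAE dose changes. Section 9.2.1.4 closes by allowing a patient who meets a stop criterion in either list to stay on drug after a benefit-risk discussion.

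**The concern.** These are stop-or-continue instructions. An investigator who follows 8.1.6 and 9.2.1.4 may restart a patient with controlled Grade 3 adrenal insufficiency. One who follows Appendix VI ends that patient's treatment. The stop is hard to undo, because section 8.1.4 bars re-initiation except for recurrence after a confirmed complete response or after elective surgery. Two similar patients at different sites could therefore be handled differently, and both sites could point to the protocol. The same holds on a smaller scale for a symptom-free Grade 4 amylase or lipase value.

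**Working it through.** No plan figure is at issue, so the check sets the rules side by side for defined patients.

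**Case 1: Grade 3 treatment-related adrenal insufficiency, controlled on physiologic replacement alone.**

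| Place | Result |
|---|---|
| 7.2.5.1 | Not a DLT, so that section's own discontinuation sentence, which excepts the listed events, does not apply |
| 8.1.6 | Restart allowed |
| 9.2.1.4 | No discontinuation required |
| Appendix VI, last row | Permanent discontinuation |

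The Appendix VI row prescribes no steroid course for adrenal insufficiency. A patient can therefore be on replacement alone at the moment when the row's stop applies, and the two sets of rules meet in the same patient at the same time. At Grade 4 there is no conflict, since 9.2.1.4 stops any Grade 4 event.

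**Case 2: Grade 4 amylase or lipase, no symptoms.** The 8.1.5.2 exception has no upper grade, so it covers Grade 4 and asks for no delay. The Grade 4 rule in 9.2.1.4 exempts no test and requires a permanent stop.

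**Case 3 (secondary): AST/ALT.** Four places give different rules:
- 7.2.5.1 treats Grade 3 or higher AST/ALT in the first 28 days as a DLT leading to discontinuation. It exempts Grade 3 that falls to Grade 1 within 7 days of starting medical management, and elsewhere allows some resumption after a DLT.
- 9.2.1.4 requires a stop above 10 x ULN, or at >5 to 10 x ULN for more than 2 weeks. With hepatic metastases it is above 8 x ULN, or above 5 x ULN for at least 14 days.
- Appendix II repeats those thresholds but says only that stopping should be considered.
- The Appendix VI hepatitis row stops at Grade 3 or above, with no minimum duration.

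The Appendix VI row directs high-dose steroids and hospitalization. The 9.2.1.4 exception for laboratory values needing neither then drops out, and its general limit of 7 days applies. For an event managed as hepatitis, the two lists therefore disagree only for elevations lasting 0 to 7 days. Taking Grade 3 as starting above 5 x ULN (an assumption, since the CTCAE limits are not printed), the band is >5 to 10 x ULN, or >5 to 8 x ULN with hepatic metastases.

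**How often.** Section 5.3.2 reports one Grade 3 hyponatremia/adrenal insufficiency event and one Grade 3 transaminase elevation among 26 exposed Part A patients. It does not say whether the first was controlled on replacement or how long the second lasted. SAP section 6 gives 5 + 5 + 5 + 10 = 25 patients in A-2, B1, B7 and B8. A forecast for them is not justified, because the Part A counts are of Grade 3 events and not of conflict cases.

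**The case against.** The strongest reply is that the lists are cumulative. The endocrine exception in 9.2.1.4 lifts only that section's own 7-day rule, Appendix VI adds further criteria for irAEs, and the closing waiver handles hard cases. Grade 3 or higher events are also AESIs (9.2.1.6), and uncertain laboratory changes go to the Medical Monitor (9.2.7).

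Part of this stands: oversight limits divergence between sites, and the waiver gives a way out. But no text makes the lists cumulative or says that the stricter governs. Section 8.1.6 also goes beyond lifting a rule, since it gives positive permission to restart. The waiver is needed only if a stop criterion is met, which is exactly what the two places dispute.

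A reader might also infer more than the documents support:
- **That the hypophysitis row conflicts in the same way.** It directs "Grade 3 or adrenal crisis: high-dose corticosteroids (methylprednisolone 1 to 2 mg/kg/day or the equivalent", so the patient is not on replacement alone when the stop applies, and 8.1.4 bars a restart after later taper.
- **That Appendix VI rejects replacement-controlled endocrinopathy altogether.** Its entry for "Grade 3 hypothyroidism: replacement therapy" only holds the drug until recovery.
- **That the liver rules diverge for up to 14 days.** That window in 9.2.1.4 needs a patient who requires neither treatment nor hospitalization, and Appendix VI directs both for Grade 3 hepatitis.
- **That the Appendix VI clauses for patients entering with Grade 2 AST/ALT are empty because inclusion criterion 15 caps both at 2.0 x ULN.** This depends on CTCAE limits that are not printed, and on screening values standing for values at entry.

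**Conclusion.** The adrenal insufficiency rules contradict each other as written, and so do the rules for asymptomatic Grade 4 amylase or lipase. Both follow from the text alone, without any assumed threshold. The AST/ALT differences are real but secondary: for an event managed as hepatitis they matter for at most 7 days, and 7.2.5.1 may also stop such a patient in the first 28 days.

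The severity is minor. The affected group is patients with Grade 3 adrenal insufficiency that is treatment-related, handled as an irAE and controlled on replacement alone, plus any with symptom-free Grade 4 amylase or lipase. A reader might infer harm to a patient or an effect on the trial's conclusions. The documents show neither: no patient is reported to have met a conflicting condition, and no endpoint, sample size or error rate depends on these rules.

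**What to change.** 1. In the last row of Appendix VI, exclude from the Grade 3 stop adrenal insufficiency that is controlled on physiologic replacement alone, and say that such patients may restart under 8.1.6. This carries over a position that 7.2.5.1, 8.1.6 and 9.2.1.4 already take.
2. In 8.1.5.2, limit the asymptomatic amylase/lipase exception to Grade 3, so that the Grade 4 stop in 9.2.1.4 stands alone.
3. For AST/ALT, the sponsor should choose one rule, with level and duration, and state it identically in 7.2.5.1, 9.2.1.4, Appendix II and Appendix VI. Which rule is a clinical choice that the documents do not settle.

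The cost is a wording amendment and a notice to sites, with no extra patients or procedures. SAP section 4 records that the trial closed early, so the change helps only patients still on treatment and any later protocol that reuses this text.
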